Research Study Proposal

Title of Study: A Prospective Study to Examine Patient Satisfaction, Function, and Limb Alignment Outcomes for Mako versus Non-Mako Total Knee Replacements

A. Background and Statement of Context

In recent years, orthopedic surgeons have increasingly embraced robotic-assisted surgical techniques to improve the accuracy and precision of total hip and knee arthroplasty, and partial knee arthroplasty. The stages of computer-assisted surgery include preoperative imaging and planning, intraoperative design and execution, and postoperative evaluation [1]. Several prior studies have attempted to validate the clinical efficacy and cost efficiency of robotic assisted total hip replacement [2-6]. However, few studies have addressed the clinical and radiographic outcomes of robotic assisted total knee arthroplasty (TKA), with no consensus in regards to meaningful clinical value [7]. In November 2015, as a pioneer user, Virtua Joint Replacement Institute (JRI) adopted the Mako System (Stryker, Kalamazoo, MI) - a robotic-arm assisted surgery technology based on CT image guided navigation. Today, 5 surgeons have performed a total of 471 TKA cases done to date using the Mako device. This study is aimed at contributing to the nascent body of literature on robotic-assisted TKA (RA-TKA) by comparing the patient reported outcomes and accuracy of implant placement for patients receiving RA-TKA versus TKA with traditional mechanical guides (MG-TKA).

B. Study Questions/Objectives and Hypotheses

Study Objectives

The purpose of this study is to compare the efficacy (patient reported outcomes and radiographic results) for RA-TKA versus MG-TKA. Specifically, when compared to their control group counterparts that undergo MG-TKA, we hypothesize that the intervention group treated with RA-TKA will, following surgery, experience:

1. Higher patient reported Forgotten Joint Score (FJS), 3 months, 6 months, 12 months, 2 years, and 5 years postoperatively (primary outcome measure).

2. Higher patient reported Knee injury and Osteoarthritis Outcome Score (KOOS), 3 months, 6 months, 12 months, 2 years, and 5 years postoperatively.

3. Higher patient reported Veterans Rand 12-item Health Survey Score (VR-12), 3 months, 6 months, 12 months, 2 years, and 5 years postoperatively.

4. Fewer radiographic outliers (deviation greater that 3 degrees from planned mechanical limb alignment). The radiographic analysis will be performed postoperatively using long limb plain radiographs.

C. Study's Alignment with Virtua's Mission, Vision, Values and Strategic Imperatives

Though the Virtua JRI remains at the forefront of RA-TKA, through this study Virtua Health may become the first health system to report better clinical outcomes of TKA utilizing RA-TKA versus the standard MG-TKA. Moreover, these data may help demonstrate greater value achieved by the application of RA-TKA in TKA practiced at Virtua, and provide an evidence-base of higher quality and value to insurers and population-based health providers.

D. Study Design

Type of Study Design

This is a randomized, controlled, prospective, single-blind study.

Study Inclusion Criteria

Patients who meet all of the following inclusion criteria may be eligible to participate in the study:

1. Age 18 or older

- 2. Diagnosed with primary osteoarthritis and cleared to undergo total knee arthroplasty at the Virtua JRI
- 3. Willing to provide informed consent, participate in study, and comply with study protocol

Study Exclusion Criteria

Patients who meet any of the following criteria may not be eligible to participate:

1. Pregnant or contemplating pregnancy prior to surgery;

2. Worker's compensation or personal injury related to knee (clinical outcomes have been shown to be less predictable and often poorer in this patient group; there may also exist potential issues with reimbursement)

3. Post-traumatic arthropathy (clinical outcomes have been shown to be less predictable; pre-operative deformity and risk factors are greater and difficult to propensity-match between groups)

 Self-pay patients or patients whose insurance are known to typically decline reimbursement for preoperative CT scans

E. Study Procedures

During the preoperative office visit, the surgeon will inform the patient that appears to meet study eligibility criteria about the study, and discuss the differences between the two surgical techniques (RA-TKA versus MG-TKA) including their potential risks and benefits. The surgeon will make clear to the patient that consenting to be a part of the study means that the patient has agreed to be randomly assigned to one of the two surgical groups. Currently at the Virtua JRI, the decision to use RA-TKA for a TKA procedure is driven by the surgeon's preference. The surgeon will therefore let it be known to the patient that the only difference the patient will experience as a result of being a part of this study is that the decision to use the Mako technology for their procedure will now be left to chance.

Patients who are deemed eligible to participate in the study and are willing to participate will be asked by the surgeon to complete the research informed consent. This document will be summarized verbally by the surgeon and potential participants will be given the opportunity to ask questions about the protocol or their involvement prior to providing consent. Those who agree to participate and provide research informed consent will be enrolled in the study, and given a copy of the research informed consent document. The patient's informed consent would be added to the patient's chart.

A computer-generated randomization scheme will be employed and the randomization outcomes will be sealed in opaque envelopes. Two to three weeks ahead of the consented patient's surgery, a JRI office staff will pick an envelope from the randomized stack, unseal the envelope, and based on the outcome (even or odd), assign the patient to one of the two surgical groups. While the study intervention group (even) will receive RA-TKA, the control group (odd) will receive MG-TKA. The office staff will inform the surgeon and Mako representative if the patient was assigned to the RA-TKA group. The patient will not be told which group they are assigned to in order to eliminate subjective bias from the self-reported patient outcomes as a result of the patients knowing what procedure they had. Because patients undergoing RA-TKA require 4 stab incisions separate from the TKA incision for pin placement, it will become obvious to patients undergoing MG-TKAs that they did not have RA-TKA. In order to blind the patient to which treatment group they have been randomized to, patients enrolled in the MG-TKA group will have 2 stab incisions made. This is similar to prior published orthopedic surgery studies where patients in the control group for arthroscopic intervention were given sham portal incisions to preserve blinding (12-13).

In line with routine pre-operative planning, all study patients will be scheduled to undergo pre-operative CT scans within 2 to 3 weeks of surgery. At their 2-week post-operative office visit, all study patients will be scheduled to undergo post-operative CT scan before their 6-week post-operative visit so that component rotation could be compared to pre-operative target values.

Anesthesiologists will use their usual pre-operative and intra-operative techniques for all study participants. Post-operative care will be standard between groups. As with standard practice, pre-operative and post-operative range of motion will be recorded.

F. Statistical Analysis and Sample Size Justification

Statistical Methods

The primary outcome measure is the difference in mean Forgotten Joint Score (FJS) between the two groups of patients for which the two sample t-test will be utilized. The FJS is a self-completed 12-item questionnaire used to assess patients' awareness of their artificial joint during activities of daily living on an awareness scale of 0 (never) to 4 (mostly). There is a 6th response of "not relevant for me", and this is treated as a missing value and not included in the number of completed items. All the responses are summed up and divided by the number of completed items, and the mean value is then multiplied by 25 to obtain a total score from 0 to 100. This score is then subtracted from 100 to change the direction of the final score in such a way that higher scores indicate a higher degree of forgetting the artificial joint [8]. The FJS (Appendix 1) will be administered to the patients during their regularly scheduled 3, 6, and 12 months, 2 year, and 5 year postoperative office visits.

A second outcome measure is the difference in Knee injury and Osteoarthritis Outcome Score (KOOS) between the two groups of patients for which the two sample t-test will also be utilized. The KOOS is a knee-specific instrument used to evaluate short-term and long-term symptoms and function in subjects with knee injury and osteoarthritis. It consists of 42 questions in 5 subscales; Pain, other Symptoms, Function in daily living (ADL), Function in Sport and Recreation (Sport/Rec), and knee-related Quality of Life (QOL). All questions are assigned a score of 0 (No Problems) to 4 (Extreme Problems). Scores are transformed to a 0 to 100 scale, with zero representing extreme knee problems and 100 representing no knee problems [9]. The KOOS will be administered to the patients during their regularly scheduled 3, 6, and 12 months, 2 year, and 5 year postoperative office visits.

A third outcome measure is the difference in mean scores for the Veterans RAND 12 Item Health Survey (VR-12) between the two groups for which the two sample t-test will be utilized. The VR-12 is a 12-item questionnaire corresponding to eight principal physical and mental health domains including general health perceptions, physical functioning, role limitations due to physical and emotional problems, bodily pain, energy-fatigue, social functioning and mental health. The 12 items are summarized into two scores: a Physical Component Score (PCS) and a Mental Component Score (MCS) which then provides an important contrast between the respondents' physical and psychological health status [10]. The VR-12 will be administered to the patients during their regularly scheduled 3, 6, and 12 months, 2 year and 5 year postoperative office visits.

The radiographic outcomes will be studied in two ways.

1) The mechanical alignment of the entire post-operative limb will be measured at 6 weeks by long-limb radiograph cassettes and compared to the pre-operative plan for accuracy and deviation less than or greater than 3 degrees from the intended target. From each treatment group, the percentage of patients with radiographic outliers (deviation greater that 3 degrees from the expected implant placement) will be compared. The z-test for proportions will be used for this assessment.

2) Pre-operative and post-operative CT scans will be performed on all patients and component rotation will be measured and compared to pre-operative target values for each. The rotational femoral component angle is defined as the angle between the surgical epicondylar axis and the posterior condylar line of the femoral component. The rotational tibial component angle is defined as the angle between a line connecting the centre of the tibial component and the medial third of the tibial tubercle and a line perpendicular to the posterior condylar line of the tibial component [14]. A Mann-Whitney U test can determine statistically significant differences (p < 0.05) in absolute value from the target angles between the two treatment groups using these parameters. Fisher's exact probability test will be used to compare the quality of implantation, measured against the ideal position, between the two systems with these parameters (p < 0.05). The correlation between error in rotational alignment and the functional score for both groups can be measured using Spearman's correlation coefficient by rank test (p < 0.05). Preoperative and postoperative posterior femoral condylar offsets will be measured in the sagittal plane for the preoperative femur and the femoral component. The maximum thicknesses of the medial and lateral posterior condyles will be measured from the edge of each condyle to a line tangential to the posterior cortex of the femoral shaft [15].

Two blinded reviewers will assess each patient film to assure intra-observer and inter-observer reliability. The chance-corrected κ -coefficient will be calculated to determine intra- and inter-observer agreement [16].

All statistical analyses will be conducted at the 0.05 level of significance.

Power/Sample Size

Giesinger et al. [11] reported that for 98 TKA study patients, their 2-month, 6-month, 1-year, and 2-year postoperative FJS mean (standard deviation) were respectively: 20.9 (17.4), 41.7 (25.9), 67.3 (27.2), and 80.8 (25.8). For the purpose of our power analysis therefore, we find it reasonable to assume a 10 point difference in mean FJS between the two patient groups as the effect size to detect and a standard deviation of 27.2. For an 80% power at a 0.05 level of significance, the minimum required sample size for each group is 118. To account for possible crossovers, we apply a 5% markup against the statistically derived sample size to arrive at a minimum of 124 patients needed for each group for a total of 248 patients to be enrolled in the study.

G. Study Duration and Subject Enrollment Feasibility

Between Jan 1, 2017 to November 16, 2017, the Virtua JRI averaged about 128 TKA cases a month. If we assume that 25% of eligible patients can be enrolled into the study, then we estimate to average about 32 study patients per month. For the 248 patients needed in total for the study therefore, we anticipate an 8-month study enrollment completion timeline.

H. Study Limitations

The main limitation we anticipate is with regards to the possibility of patients declining to participate in the study due to concerns of leaving their surgical assignment to chance. By assuming only a 25%

enrollment rate however, combined with the large volume of TKA cases we see at the Virtua JRI, the projected 8-month enrollment completion timeline is very realistic.

I. Stakeholder Communication Plan

The physician assistants (PAs) will play a crucial role in enrolling patients for the study. All the PA's at the Virtua JRI will be trained on the study protocol so that they are well equipped to address patients' questions/concerns. The PAs will also take the lead on administering the patient reported outcomes surveys (FJS, KOOS, VR-12) and they will receive the relevant training to administer these effectively.

J. Dissemination Plan for Study Findings

The Virtua JRI surgeons plan to publish the study outcomes in a reputable peer-reviewed orthopedic journal such as the Journal of Arthroplasty.

K. Itemized Study Budget

Department	Estimated Labor Hours	Estimated Supply Cost (\$)
Virtua Clinical Research Department	80	
– Statistical/IRB/Manuscript support		
Virtua Voorhees Radiology		\$24,800 (Estimated \$100 per post- operative CT scan for 248 study patients)

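### The primary outcome is FJS at five visits with no primary visit or success rule, so neither the 0.05 level nor the 80% power attaches to a defined primary claim

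*Combined protocol and SAP*

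**What the plan says.** Section B, objective 1, places five FJS assessments under one primary label: "Higher patient reported Forgotten Joint Score (FJS), 3 months, 6 months, 12 months, 2 years, and 5 years postoperatively (primary outcome measure").

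Section F, Statistical Methods, defines the primary outcome as the "difference in mean Forgotten Joint Score (FJS) between the two groups of patients for which the two sample t-test will be utilized". It names no visit there and then lists the same five: "The FJS (Appendix 1) will be administered to the patients during their regularly scheduled 3, 6, and 12 months, 2 year, and 5 year" postoperative visits. The section closes with a blanket rule: "All statistical analyses will be conducted at the 0.05 level of significance".

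Section F, Power/Sample Size, cites a study of 98 TKA patients, whose FJS means (SDs) at 6 months, 1 year and 2 years were "41.7 (25.9), 67.3 (27.2), and 80.8 (25.8"). It then assumes "a 10 point difference in mean FJS between the two patient groups as the effect size to detect and a standard deviation of 27.2", again with no visit attached, and concludes: "For an 80% power at a 0.05 level of significance, the minimum required sample size for each group is 118". A 5% markup for crossovers brings this to 124 per group, 248 in total.

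Nowhere do the documents give a primary time point, a rule for combining the five visits, a testing order, an adjusted significance level, or a repeated-measures summary.

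**The concern.** A two-sample t-test compares one value per patient. It cannot be run on FJS until a visit or a summary over visits has been chosen, and the plan leaves that choice open. A t-test at each visit is the natural reading of objective 1 with Section F, but it is an inference; the documents do not say so.

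The text allows at least two success rules, and they fail in opposite directions. If any significant visit counts, or the visit is picked once results are known, 0.05 is not the error rate of the primary claim. If all five must be significant, the error is far below 5%, but 80% is not the power of the primary claim. A mixed result, such as significance at 6 months only, could be reported as success or as failure. The visits run from 3 months to 5 years, so early results could be known years before the last visit.

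**Working it through.** **Inputs from Section F.** Difference 10; SD 27.2; 118 per group; level 0.05; cited SDs 25.9 (6 months), 27.2 (1 year) and 25.8 (2 years). Five visits, from Section B.

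**Assumptions.** The documents give no between-visit FJS correlation, so 0 to 0.9 is used, with exchangeable and AR(1) structures. Data are taken as complete at every visit, so the five test statistics share the correlation of the scores.

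**1. The plan's own figure.** By the normal formula, n = 2 × (1.960 + 0.842)² × 27.2² / 10² = 116.1, so 117. With the t distribution it is 117.1, so 118, as stated. Power at 118 is 80.3%; at 117 it is 79.96%. A one-sided test would need only 93. The 118 is therefore right for exactly one two-sided t-test. The markup also checks: 118 × 1.05 = 123.9, so 124.

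**2. Any-visit rule.** With independent visits, the two-sided familywise error is 1 − 0.95⁵ = 22.6%. Objective 1 is directional, so the more relevant error is a false result for RA-TKA: 1 − 0.975⁵ = 11.9%. For correlated visits, 2,000,000 five-variate normal vectors were simulated per setting, counting any |z| > 1.96 and any z > 1.96.

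**3. All-five rule.** With a true 10-point difference, each z statistic has mean 10 / (27.2 × √(2/118)) = 2.82. The chance that one exceeds 1.96 is 0.806, so with independent visits all five do so with probability 0.806⁵ = 34%. Correlated cases were simulated as above, counting all five z > 1.96.

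| Assumed correlation | Any visit: two-sided error | Any visit: falsely favours RA-TKA | All five: power at 118 |
|---|---|---|---|
| 0 | 22.6% | 11.9% | 34% |
| 0.4 | 19.7-21.1% | 9.9-10.8% | 43-49% |
| 0.8 | about 13-15% | 6.4-7.5% | 59-64% |
| 0.9 | 10.2-11.9% | 5.1-5.9% | 66-70% |
| One test, for reference | 5% | 2.5% | 80.3% (one visit) |

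Ranges span the two correlation structures. Under the all-five rule, the chance of falsely favouring RA-TKA is only 0.001-0.42% at correlations 0.4 to 0.8.

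**4. Sensitivity of the all-five power to the SD.** With the cited SDs at 6 months and 2 years, and 27.2 kept at 3 months and 5 years, power is 37-71% over correlations 0 to 0.9. A more favourable case, with 17.4 (the cited 2-month SD) at 3 months and 25.8 at 5 years, gives about 48-75%.

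**5. One pre-named visit, two-sided 0.05, 118 per group (noncentral t).** Power is 84.0% at 6 months (SD 25.9), 80.3% at 12 months (SD 27.2) and 84.3% at 2 years (SD 25.8). No SD is cited for 3 months or 5 years.

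**The case against.** The best counter-argument is that the plan does have a single test in mind. Section F speaks of one difference and one t-test, the 118 reproduces as one two-sided comparison, and 27.2 is the cited 1-year SD, which hints at 12 months. On this view only the visit is unstated, and both success rules are the reader's constructions. It is fair that the sample-size arithmetic is sound and that neither rule is written in the plan. But 27.2 is also the largest of the four cited SDs, so it may simply be the cautious choice, and a visit that has to be guessed is not prespecified. Objective 1 gives all five visits the primary label.

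A second objection is that 22.6% overstates the problem, because repeated scores from the same patients are correlated and the hypothesis is directional. That is right as to emphasis: the directional figures at positive correlations are the ones to weigh. Even at 0.9 they are about twice the 2.5% of a single test.

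A third is that using 27.2 at every visit is pessimistic for the all-five power. Smaller SDs do help, but the most favourable case tried still reaches only about 75%.

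One further point stands in full: the single-visit powers assume complete data. The 5% markup is for crossovers, not loss to follow-up, and at SD 27.2 power falls just below 80% once fewer than 118 per group are analysed.

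**Conclusion.** The concern holds and must be fixed before outcomes are examined. The plan's 0.05 and 80% are both correct for one FJS comparison, but the plan does not say which one, while five carry the primary label. Testing visit by visit loses one figure or the other at every correlation tried. Under an any-visit rule, false claims for RA-TKA run from 11.9% down to about 5%, against 2.5%. Under an all-five rule, power runs from 34% up to 70%, against 80%. These ranges rest on assumed correlations of 0 to 0.9, complete data and, for the power figures, a 10-point effect with SD 27.2 at every visit. The conclusion does not depend on where in the ranges the truth lies.

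**What to change.** Before outcomes are examined, name one FJS visit in Section B (objective 1) and in both parts of Section F as the single primary endpoint, tested two-sided at 0.05. Make the other four FJS visits secondary; KOOS and VR-12 remain secondary.

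Any one pre-named visit restores the 5% level. Twelve months is the natural option, because its cited SD is the one behind the 118; n then stays at 118, or 124 with the markup. Six months or 2 years would also keep at least 80% power with 118 analysed per group. Choosing 3 months or 5 years would require a stated SD assumption.

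The change costs protocol wording only, with no extra patients, visits or data. The downside is that a significant FJS result at another visit could no longer be called the primary result.

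Keeping all five visits primary costs more. An any-visit rule with Bonferroni (0.05 / 5 = 0.01 per visit) needs 175 per group for 80% power at a given visit, 184 with the same markup; at 118 per group that power is 59%. An all-five rule needs about 147 to 200 per group before markup, for correlations 0.9 to 0.

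### Section E has the surgeon say that chance assignment of Mako is the only difference from taking part, yet it prescribes two blinding-only stab incisions for control patients

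*Combined protocol and SAP*

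**What the plan says.** Everything relevant is in Section E, Study Procedures, apart from the arm sizes, which are in Section F under Power/Sample Size.

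- **What the surgeon conveys before consent.** Section E notes that the surgeon's preference currently decides whether the robot is used. The surgeon is then to convey one change, which the protocol introduces as "the only difference the patient will experience as a result of being a part of this study". The change it names concerns who chooses the technique, in these words: "the decision to use the Mako technology for their procedure will now be left to chance".
- **The consent document.** The next paragraph covers the research consent form: "This document will be summarized verbally by the surgeon". Patients may ask questions and receive a copy.
- **Blinding.** After the randomization procedure, the section says: "The patient will not be told which group they are assigned to". It explains that "patients undergoing RA-TKA require 4 stab incisions separate from the TKA incision for pin placement", and that because of this "it will become obvious to patients undergoing MG-TKAs that they did not have RA-TKA".
- **The remedy.** To keep the blind, "patients enrolled in the MG-TKA group will have 2 stab incisions made". The precedent offered is earlier surgical trials in which "patients in the control group for arthroscopic intervention were given sham portal incisions to preserve blinding".
- **Size.** Section F plans at least 124 patients per group, 248 in total.

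**The concern.** The surgeon's statement is worded as complete: it speaks of the *only* difference that a participant will experience from being in the study. Shortly afterwards the same section adds a skin incision procedure for one arm that serves the trial and not the patient's operation. A patient assigned to conventional surgery would experience that difference, and it is not the chance assignment that the statement describes.

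At stake is the accuracy of what patients are told before they agree to take part. The surgeon would be following the protocol in giving an account of participation that the protocol itself contradicts. No estimate of the treatment effect depends on it.

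**Working it through.** The check is a comparison of text, with one figure for scale.

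**1. What the sentence covers.** It opens as a consequence of the preceding remark about surgeon preference, so its main purpose is to say who now chooses the technique. Its wording goes further: it concerns what the patient experiences through participation, and it names a single item.

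**2. Are the control-arm incisions part of ordinary MG-TKA?** The protocol's own reasoning says they are not. It argues that, without added incisions, it is clear to MG-TKA patients which operation they had: "it will become obvious to patients undergoing MG-TKAs that they did not have RA-TKA". That argument works only if ordinary MG-TKA leaves no such marks.

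**3. Do they have a surgical purpose?** In RA-TKA the stab incisions hold pins. For MG-TKA the only reason given is blinding, supported by the sham-incision precedent.

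**4. Side by side.**

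| | Surgeon's statement | Procedure for MG-TKA |
|---|---|---|
| What participation changes | Choice of technique, now by chance | Choice of technique, now by chance |
| Anything else? | None, by the word *only* | Two stab incisions for blinding |

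The second row conflicts.

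**5. How many patients.** Inputs from Section F: difference 10 points, SD 27.2, power 80%, significance level 0.05. The level is taken as two-sided, because sidedness is not stated; a one-sided calculation gives 92 per group and does not match the plan.

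- Normal approximation: n = 2 × (1.960 + 0.842)² × 27.2² / 10² = 116.1, rounded up to 117 per group.
- t-test solution: 117.1, rounded up to 118 per group, which is the plan's figure.
- With the 5% markup: 118 × 1.05 = 123.9, rounded up to 124 per group; 2 × 124 = 248.

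The planned control arm is therefore 124 / 248 = 50% of participants. I write *about* 124 because the plan states it as a minimum and does not describe a scheme that guarantees equal arms.

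**The case against.** The strongest reply has four parts.

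- **Context.** The sentence answers one question, namely who picks the technique, and should not be read as a full list. This is a fair account of its purpose, and it is a reason to keep the severity low. It does not make the wording accurate.
- **Other discussion.** The surgeon must also go over both techniques with their risks and benefits, so patients hear more than this sentence. That is true. But the blinding incisions belong to neither technique, so a discussion of the techniques need not reach them.
- **The consent form.** That document is the instrument of disclosure, and it may describe the incisions. This stands, and it limits the point. If the form discloses them, the surgeon's statement is at odds with the form that the surgeon summarizes. If it does not, the statement is still inaccurate. Either way the sentence needs changing.
- **Openness.** The protocol states the incisions plainly, gives the reason and cites precedent. This also stands. The choice to use sham incisions is not challenged here, and the protocol gives the message in paraphrase, not as a verbatim script.

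A reader might infer that consent was deficient or that patients are misled. The documents do not support that, because the consent form is not in the text. A reader might also count the undisclosed assignment and the post-operative CT as further breaches of the *only difference* statement. The protocol does not say what patients outside the study are told about technique, and does not say outright that the scan is outside usual care, so neither is relied on.

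**Conclusion.** The point holds as a mismatch between an instruction and a procedure in the same section. The surgeon is directed to name chance assignment as the sole difference, while patients in the control arm, about 124 of 248 planned, receive two stab incisions whose only stated purpose is blinding.

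This rests on two readings of the protocol: that ordinary MG-TKA has no such incisions, which follows from its own blinding argument, and that the incisions have no purpose beyond the one stated.

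The number of patients shows the reach of the inaccuracy and does not measure harm. A reader might infer an excess of complications, but the documents give no complication rate for these incisions. Nor does anything here change the Forgotten Joint Score endpoint, the sample size, the power or the analysis. Severity: minor wording correction, worth making because it concerns what patients are told before consent.

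**What to change.** Replace the *only difference* sentence in Section E with one statement, worded identically for every patient and consistent with the consent document. For example: *The technique will be chosen by chance and you will not be told which one you had. Small stab incisions are made in both groups; in one group they are made only so that patients cannot tell which operation they received.*

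The number per arm should be left out of the statement. The arms differ (4 versus 2), so a patient who knew the numbers could work out the assignment, and the primary outcome is self-reported.

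Costs:

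- **Administrative.** A protocol wording change with IRB notification, plus a change to the consent form if it lacks this information.
- **Recruitment.** Consent may fall slightly. On the plan's arithmetic, 128 cases a month × 25% = 32 patients a month, and 248 / 32 = 7.75 months. If the rate were 22.5% or 20%, which are assumed values with no basis in the documents, enrolment would take 248 / 28.8 = 8.6 or 248 / 25.6 = 9.7 months.
- **Blinding.** There is a small risk that the statement draws attention to the incisions. Leaving out the numbers limits it.

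The design, sample size and analysis stay as they are.

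### The allocation procedure states no envelope numbering, opening order, patient linkage or log, so adherence to the random sequence could not be verified; adding surgeon to the patient-reported outcome analyses is a related, modest gain

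*Combined protocol and SAP*

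**What the plan says.** The allocation procedure is in E. Study Procedures. It begins: "A computer-generated randomization scheme will be employed and the randomization outcomes will be sealed in opaque envelopes". The envelope is opened "Two to three weeks ahead of the consented patient's surgery", when "a JRI office staff will pick an envelope from the randomized stack, unseal the envelope, and based on the outcome (even or odd") the patient goes to the robotic-assisted (RA-TKA) or mechanical-guide (MG-TKA) group. The staff member then tells the surgeon and the device representative if the result is RA-TKA. The patient is not told.

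No section gives envelope numbers, a rule for which envelope comes next, a step that ties an envelope to a patient before it is opened, a log, retention of opened envelopes, block sizes or strata.

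Three other places bear on this:
- E. Study Procedures says that in current practice "the decision to use RA-TKA for a TKA procedure is driven by the surgeon" and that surgeon's preference.
- A. Background reports that "Today, 5 surgeons have performed a total of 471 TKA cases done to date using the Mako device".
- F. Statistical Analysis compares FJS, KOOS and VR-12 between groups by two-sample t-tests. Surgeon appears in none of the analyses.

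**The concern.** A computer-generated sequence protects a trial to the extent that each consented patient receives the next assignment in it, and that this can be shown afterwards. The stated procedure supplies the sequence and the concealment, but no means of showing that the sequence was followed. If an envelope were opened and set aside, or a second one taken, nothing in the described records would reveal it.

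The setting makes this worth closing off. The envelopes are handled by staff of the same institute whose surgeons have until now chosen the technique. Opening falls weeks before surgery, which leaves time to revisit an unwelcome result. Selective use, if it occurred, would shift the primary FJS comparison in a way that a t-test cannot detect.

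The second, smaller matter is that surgeon plausibly affects outcome. With no surgeon term, any between-surgeon variation stays in the error term of the patient-reported comparisons.

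**Working it through.** **Inputs from Power/Sample Size:** difference to detect 10 FJS points, SD 27.2, alpha 0.05, power 80%, 118 per group, 5% markup, 124 per group and 248 in total. Sidedness is not stated.

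**1. The plan's own figure.** A two-sided two-sample t-test with 10/27.2 = 0.368 SD needs 117.1 per group, rounded up to 118. A one-sided test would need 92 (normal approximation), so two-sided is the reading that fits. 118 × 1.05 = 123.9, rounded up to 124; 2 × 124 = 248. The sample size reproduces, and nothing below changes it.

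**2. What a bias would do (illustrative).** SE = 27.2 × √(2/118) = 3.54. With a bias of b points and no true effect, the two-sided rejection rate is 1 − Φ(1.96 − b/SE) + Φ(−1.96 − b/SE).

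| Assumed bias b | b/SE | Type I error |
|---|---|---|
| 0.5 | 0.141 | 5.2% |
| 1 | 0.282 | 5.9% |
| 2 | 0.565 | 8.7% |
| 3 | 0.847 | 13.5% |

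The bias is roughly the share of patients steered times the gap in expected FJS between those steered to each arm. For example, 10% steered with a 20-point gap gives 0.10 × 20 = 2 points. The documents give neither quantity.

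**3. What a surgeon term would gain.** Suppose surgeon explains a share s of FJS variance. The residual SD is then 27.2 × √(1 − s). Power at 118 per arm comes from the noncentral t with 234 degrees of freedom; the few lost to the surgeon term are ignored.

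| Assumed s | Residual SD | Noncentrality, 10/(SD × √(2/118)) | Power |
|---|---|---|---|
| 0 | 27.20 | 2.824 | 80.3% |
| 2% | 26.93 | 2.853 | 81.1% |
| 10% | 25.80 | 2.977 | 84.2% |

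The gain is 0.8 to 3.9 percentage points.

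**4. Chance imbalance by surgeon.** Five trial surgeons are assumed. In simulated allocations of 248 patients, the chance that at least one surgeon has a 60:40 split or worse is 52% to 78%, depending on caseload shares (also assumed) and on whether the stack is simple randomization or a fixed 124 + 124. The effect on the estimate is small. Its SD is about 27.2 × √s × √(2/124), which is 0.35 points at s = 1% and 1.09 points at s = 10%, against a 10-point target.

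**The case against.** The strongest reply is that the plan's silence is being read against it. Four stronger readings are tempting, and the documents support none of them.

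- **That the envelopes are unnumbered and staff may take whichever they like.** The text says neither. Taking the top envelope of a stack already in random order fits the wording equally well. All that can be said is that no numbering or order is stated.
- **That the computer-generated sequence therefore does not govern allocation.** This does not follow. The envelopes are sealed and opaque, so a blind pick in any order is random. The patient has already consented, office staff rather than the surgeon open the envelope, and the surgeon hears the result afterwards. Subversion would need a deliberate act, and nothing suggests one.
- **That imbalance between surgeons confounds the comparison.** Unstratified 1:1 randomization is valid. Chance imbalance by surgeon neither biases the t-test nor inflates its type I error; it is random error that the standard error already reflects. The five surgeons in A. Background are past users of the device, and the number operating in the trial is not given.
- **That 8.7% is the expected error rate.** It is one scenario built on two assumed inputs; the range above is the fairer statement.

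It can also be objected that separate blocked envelope sets per surgeon carry a cost. The surgeons who consent patients also learn assignments, so each could partly predict the next one in their own set. A single common stack is harder to predict. This stands, and it is why stratification is only optional below.

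What survives these replies is that a departure from the sequence would be invisible, and that a simple written procedure would make it visible.

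**Conclusion.** The point holds as a cheap improvement to be made. The stated procedure can give a valid random allocation, but it gives the trial no way to show that the sequence was followed, and a failure of this kind cannot be repaired after the envelopes have been used. No bias is shown. Its possible size rests wholly on an assumed steering rate and an assumed prognostic gap, with type I error of 5.2% to 13.5% for a bias of 0.5 to 3 points.

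The surgeon term is secondary. It is worth about 1 to 4 percentage points of power at 118 per arm, on the assumption that surgeon explains 2% to 10% of FJS variance. The documents give no figure for that share.

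**What to change.** Amend the allocation paragraph in E. Study Procedures to state that:
1. opaque envelopes are numbered sequentially and prepared by staff outside the JRI clinic; the Clinical Research Department, already budgeted for statistical support, is one candidate;
2. office staff open only the next number, after writing the patient ID and date on the unopened envelope;
3. all envelopes, used and unused, are kept with a log that can be reconciled against the generated list.

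If such numbering and logging already exist, describing them in the protocol settles this part.

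In F. Statistical Analysis, replace the unadjusted t-tests for FJS, KOOS and VR-12 with a linear model containing treatment and surgeon. The radiographic comparisons are not covered by this proposal, and no gain has been worked out for them.

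Stratifying by surgeon is optional. If it is used, block sizes should vary and not be disclosed, because surgeons who consent patients also learn assignments.

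The cost is envelope labelling, a log sheet and one model term. The sample size of 248 does not change. The documents do not say whether enrolment has begun; if it has, the procedure can apply only to envelopes not yet opened.
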